5.2. Baseline (day 1, same day as screening evaluation)

At baseline, the following procedures will be carried out:

1. Collection of two nasopharyngeal swabs (one from each nostril) using nylon flocked dry swabs (Copan Diagnostics) for RT-PCR and culture.
2. Collection of blood sample for laboratory safety tests.
3. Collection of a urine sample for routine urinalysis (glucose, protein and blood).
4. Review and recording of any concomitant medications.
5. Provision of an electronic diary to subject via his/her own smartphone or a provisioned device, and subject completion of baseline electronic diary under supervision and instruction of study site personnel, including the Practice Diary, FLU-PRO Questionnaire, Activity Diary, and Study Drug Intake and Temperature Diary.
6. Randomization and dispensing of study medication (medication assigned in sequential order).

7. Administration of the first dose of study medication with food (< 1 hour after food intake) under observation of Investigator or a member of Investigator's staff, and entry in Study Drug Intake and Temperature Diary.
8. Instruct subject regarding:
 - a. *Administration of study medication.* Subjects will be instructed to take the study medication (two tablets) twice daily with food (< 1 hour after food intake, preferably a high-fat meal but at a minimum a cereal bar). The subject should take his/her second dose as close as possible to 12 hours after the first dose. Then he/she will take the study medication every 12 hours for the remaining 4 days.
 - b. *Completion of subject diary.* Subjects will be instructed on completion of the electronic diary.
 - c. *Use of birth control.* Female subjects of childbearing potential, if sexually active, will be instructed to continue an acceptable method of birth control for the duration of the study and for 1 month post-treatment. Acceptable methods of birth control include a double barrier method, oral birth control pills, an IUD, or medroxyprogesterone acetate administered intramuscularly.
 - d. *Follow-up visits:* Subjects will be instructed to return to the clinic for follow-up on Day 7 and Day 22.
 - e. *Seeking emergency care or contacting the study physician or nurse:* Subjects must be informed to seek emergency medical care or contact the study physician or nurse if they develop any of the following symptoms listed below during the full 22-day study and follow-up period.

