8. STATISTICAL CONSIDERATIONS

8.1. Sample Size Calculations

The Symptom Response definitions for this study will be derived from the subjects' FLU-PRO questionnaire responses as described in section 8.3 below. The FLU-PRO-derived endpoint is expected to track very closely to return to usual health status (a daily yes/no question in the FLU-PRO questionnaire), which in turn is expected to track very closely to ability to perform 100% of normal activities. We assume, therefore, that the cumulative distributions of time to Symptom Response for the placebo treatment group will closely reflect historical data from Romark Study RM08-3002 for time from first dose until the EV/RV-infected subjects report that they are able to perform 100% of usual activities (see placebo curve in chart below). Then, to calculate sample size, we assume that treatment with NTZ treatment should result in reduction of at least 48 hours in median time to symptom response. The following curves have been developed for determining sample size.

Based upon these curves, a sample size of 530 subjects with laboratory-confirmed EV/RV infection (i.e. 265 for each of the 2 groups) will provide 90% power to detect a statistically significant difference in the survival distributions between the NTZ and placebo groups (2-sided alpha of 0.05). This calculation was performed for the Gehan rank test using SAS PROC POWER (SAS 9.4) with the curves shown above (proportion not recovering by the end of each day was used as input) and censoring at day 21 (hour 504). Assuming that up to 12% of subjects will have incomplete data, we arrive at a sample size of 600 subjects in total, 300 per treatment group to yield at least approximately 530 with complete data (all 600 subjects will be included in the primary analysis with subjects with incomplete data censored as of their last entry).

Based upon these calculations, the study will enroll at least 600 subjects with laboratory-confirmed EV/RV infection up to a maximum of 700 subjects with laboratory-confirmed EV/RV infection. We estimate that this will require enrollment of up to 1,750 subjects in total assuming an EV/RV-positive rate of at least 40%.

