#### **11.2.2. Analysis of the Primary Efficacy Parameter**

The primary efficacy parameter, time to Symptom Response, will be derived as follows:

Event: Time of Symptom Response – time of the first dose

Censored: Time of last symptom assessment – time of the first dose

If Symptom Response is achieved at the time of the first symptom assessment diary record, the subject will be excluded from the analysis.

If Symptom Response is not achieved prior to a subject’s last available diary assessment, but the criteria are met at the last available diary assessment with no evidence of symptom relief medication intake during that diary period, time of Symptom Response will be considered to have occurred at the start of the last daily diary period.

Time to Symptom Response for the NTZ treatment group will be compared to that of the placebo treatment group using a Gehan-Wilcoxon test stratified by (1) time from onset of illness to time of first dose of study medication (0-24, >24-≤36, or >36 hours from onset), (2) pre-enrollment use of symptom relief medication, and (3) presence of underlying lung condition including asthma, COPD, or past or present history of smoking. The comparison will be graphically depicted using Kaplan-Meier curves.

Analysis Population(s): ITTI

Derived Variables: Event: Time of Symptom Response – time of first dose

Censored: Time of last symptom assessment – time of first dose

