### 11.6.2. Analysis of Time to Symptom Response by Symptom Relief Medication Use for Placebo-Treated Subjects

Repeat the primary efficacy analysis for the ITTI and ITT populations comparing placebo-treated subjects who did not use symptom relief medication to placebo-treated subjects who did use symptom relief medication. Sum of baseline FLU-PRO symptom assessments (<42 or  $\geq$ 42) will be included as a factor in the analysis. Pre-enrollment symptom relief medication use will not be used as a factor in the analysis since the groups being compared are classified by symptom relief medication use.

Analysis Population(s): ITTI placebo-treated subjects, ITT placebo-treated subjects

Derived Variables: See Section 11.2: Primary Efficacy Analysis

**11.6.3. Analysis of Time to Ability to Perform All Normal Activities by Symptom Relief Medication Use for Placebo-Treated Subjects**

Repeat the analysis of time to ability to perform all normal activities for the ITTI and ITT populations comparing placebo-treated subjects who did not use symptom relief medication to placebo-treated subjects who did use symptom relief medication. Sum of baseline FLU-PRO symptom assessments ( $<42$  or  $\geq 42$ ) will be included as a factor in the analysis. Pre-enrollment symptom relief medication use will not be used as a factor in the analysis since the groups being compared are classified by symptom relief medication use.

Analysis Population(s): ITTI placebo-treated subjects, ITT placebo-treated subjects

Derived Variables: See Section 11.4.1 Time to Ability to Perform All Normal Activities

**11.6.4. Proportion of Subjects Experiencing Complications of Colds by Symptom Relief Medication Use for Placebo-Treated Subjects**

Repeat the analysis of proportion of subjects experiencing complications of colds for the ITTI and ITT populations comparing placebo-treated subjects who did not use symptom relief medication to placebo-treated subjects who did use symptom relief medication using a Fisher's exact test.

Analysis Population(s): ITTI placebo-treated subjects, ITT placebo-treated subjects

Derived Variables: None

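### Baseline FLU-PRO severity is collected before dosing, but it is neither tabulated by arm nor adjusted for in the primary comparison or any sensitivity analysis

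*SAP*

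**What the plan says.** Protocol 5.2 lists, as step 5 of the baseline visit, "subject completion of baseline electronic diary under supervision and instruction of study site personnel", and that diary includes the FLU-PRO questionnaire. Randomization is step 6 and the first dose is step 7. SAP Table 6 codes 32 items from 0 to 4 and states that no item can be missing within a completed record. A baseline total from 0 to 128 therefore exists for every completed baseline diary.

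SAP 11.2.2 compares the arms "using a Gehan-Wilcoxon test stratified by (1) time from onset of illness to time of first dose of study medication", with pre-enrollment symptom relief medication and underlying lung condition as the other two factors. That makes 3 x 2 x 2 = 12 strata. Protocol 8.4.1 ties the analysis strata to those used for randomization.

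The three sensitivity analyses in SAP 11.3 concern discontinuations, the per-protocol subset and chromaturia; none uses baseline severity. SAP 10.1.4 tabulates only time since onset and virus infection.

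The baseline sum is used in SAP 11.6.2 and 11.6.3. There, split at 42, it "will be included as a factor in the analysis" of users against non-users of relief medication among placebo-treated subjects.

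**The concern.** Symptom Response requires all 32 items to be at or below their thresholds on two consecutive diaries. A subject who starts with higher scores has further to fall, so the baseline total is plausibly prognostic. That is an inference; the documents give no figure for it.

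If it is prognostic, two things follow. Variation that could be removed stays in the primary test. And if the arms differ in severity by chance, the primary result carries that difference, and no planned table or analysis would reveal it.

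**Working it through.** **Inputs from the documents.** Protocol 8.1 states "2-sided alpha of 0.05" and says that "a sample size of 530 subjects with laboratory-confirmed EV/RV infection" "will provide 90% power to detect a statistically significant difference in the survival distributions". It assumes a "reduction of at least 48 hours in median time to symptom response", censoring at 504 h and 12% incomplete data. On method it says: "This calculation was performed for the Gehan rank test using SAS PROC POWER (SAS 9.4) with the curves shown above". Strata and covariates are not mentioned. Protocol Table 7 gives a placebo median of 302 h for return to normal activities, the distribution used as a proxy.

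**The plan's own figure.** 530 / (1 - 0.12) = 602.3, or 603 rounded up, against the stated 600, so the inflation reproduces closely. The 90% cannot be checked, because the curves are in a figure that is not shown. Stand-in curves do not settle it: exponential medians of 302 and 254 h give about 39% (log-rank), and both Table 7 curves give about 96% (Gehan). I take 90% as given.

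**Formula.** Let r be the correlation of the baseline total with the Wilcoxon score within strata. Adjustment cuts the variance of the statistic by the factor (1 - r²), so

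power = Φ[(1.960 + 1.282) / √(1 - r²) - 1.960].

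- r = 0.1: 90.3%
- r = 0.2: 91.1%
- r = 0.3: 3.242 / 0.954 - 1.960 = 1.438, giving 92.5%
- r = 0.4: 94.3%

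**Simulation.** Assumed: 600 subjects, 12 strata, exponential times, placebo median 300 h, 12% drop-out, treatment hazard ratio 1.38 to 1.39. Prentice-Wilcoxon scores were tested without and with regression on the continuous baseline score. Run A used 3,000 trials per setting and 490 h of follow-up; run B used 2,000 and 504 h. The hazard ratio is for response, per SD of higher baseline score.

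| Assumed HR per SD | Run A: without, with | Gap | Run B: without, with | Gap |
|---|---|---|---|---|
| none | 88.6%, 88.6% | 0.0 | 87.3%, 86.9% | -0.4 |
| 0.85 | not run | | 87.2%, 88.0% | +0.8 |
| 0.74 | 85.6%, 87.4% | +1.8 | 84.6%, 86.1% | +1.5 |
| 0.61 | 82.8%, 87.4% | +4.6 | 81.0%, 86.4% | +5.4 |

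Repeated with Gehan scores, the test the plan names, the difference is within simulation noise for none and 0.85, about +2 points at 0.74, and +3 to +4 at 0.61. Type I error is near 5% throughout (4.7% in run A; 4.1 to 4.9% with adjustment in run B).

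Only the gap within a row is informative. Unadjusted power falls down the table because the conditional treatment effect is held fixed, whereas the plan's historical placebo curve already contains severity variation.

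**Link to the formula.** For run A at 0.74 the power quantiles plus 1.960 are 3.023 and 3.106, so r² = 1 - (3.023 / 3.106)² = 0.053 and r is about 0.23. At 0.61 they are 2.906 and 3.106, so r is about 0.35.

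**Severity as an extra stratum (24 cells).** In run B the changes were about -1.2, -1.2, -0.4 and +2.5 points over the four settings. Weak prognosis makes this route a net loss.

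**Chance imbalance.** With 300 per arm and an assumed 50/50 severity split, the SE of the between-arm difference in the high-severity share is √(2 x 0.25 / 300) = 4.1 points, so the 95% range is ±8.0. An 8-point difference shifts the log hazard ratio by 0.08 x ln(severity HR): 0.018, 0.032 or 0.055 for a high/low hazard ratio of 1.25, 1.5 or 2.0. Against ln(1.38) = 0.322, roughly the effect needed for 90% power, that is 6%, 10% or 17%.

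**The case against.** The strongest reply is that nothing is broken. The randomized, stratified test is valid without a severity term, and its strata follow the protocol. That stands.

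A reader might infer that the SAP contradicts itself by adjusting in 11.6.2 and not in 11.2.2. The documents do not support this. Section 11.6.2 compares groups that were not randomized, and severity may be why some took medication, so adjustment there addresses confounding. Its use shows only that the score is available.

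The size is also open to challenge, and much of that challenge stands:

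- A hazard ratio of 1.39 on a 300 h exponential median means 300 - 300 / 1.39 = 84 h, more than the plan's minimum of 48 h. It was chosen to bring power near 90%.
- Pre-enrollment relief medication may already stand in for severity. With an assumed correlation of 0.4 between severity and the strata, gains of about 1.5 and 4.5 points fell to about 0.9 and 3.4.
- Enrolment may reach 700. Scaling from 90% at 600 gives Φ(3.242 x √(700/600) - 1.960), about 94%, comparable to the upper-end gain.

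None of this answers the absence of any display by arm or any adjusted supportive analysis.

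**Conclusion.** The point holds as a cheap improvement. Baseline severity is measured before dosing and then plays no part in the randomized comparison or its baseline table, so a chance imbalance would go unseen and uncorrected.

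A reader might go further and say that the plan gives up a few points of power. That cannot be derived from the documents, which give no prognostic strength. The gain is about 0 if severity is weakly prognostic, about 1 to 2 points at an assumed 0.74 per SD, and about 3 to 5 points at 0.61. These figures also rest on assumed stratum shares, exponential times and a treatment hazard ratio near 1.39. Nor is there any threat to validity: type I error stays near 5% with or without the covariate.

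**What to change.** Before unblinding:

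1. In SAP 10.1.4, add the baseline FLU-PRO total by arm for the ITT and ITTI populations.
2. In SAP 11.3, add as the first supportive analysis the stratified Gehan-Wilcoxon comparison with scores adjusted by linear regression on the continuous baseline total. Use one common slope after centring within the existing 12 strata. Separate slopes are not practical: under assumed shares of 12%, 40% and 30%, one cell holds 600 x 0.12 x 0.4 x 0.3, or about 9 subjects. State how a subject without a baseline diary is handled.
3. Do not carry over the cut at 42, which has no stated rationale, and do not add severity as a stratum.

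The cost is two short SAP passages, a small program and one more analysis to explain; no new data are needed. This form guards interpretation against imbalance but leaves primary power unchanged. To gain the power, the adjusted test would have to become primary, with a matching amendment to Protocol 8.4.1.

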Based on the Phase 2 studies, two parallel Phase 3 studies of pleconaril were designed to evaluate efficacy using time to alleviation of symptoms as a primary endpoint. Symptom alleviation was defined as rhinorrhea graded absent and the other five symptoms graded absent or mild for 48 hours without the use of symptom relief medication. Enrollment was restricted to subjects presenting to the clinic within 24 hours of symptom onset. Other important subject selection criteria included otherwise healthy subjects at least 18 years of age with moderate to severe rhinorrhea and at least one other moderate or severe respiratory symptom (nasal congestion, cough, or sore throat). Subjects were excluded if they had fever, recent history of allergic rhinitis, if they had received asthma treatment within the previous two months, or if they had chronic cough, any known immunodeficiency, or any underlying medical condition that would confound study results. Enrollment was stratified based on smoking status and pre-treatment use of symptom relief medication, and subjects were allowed to take acetaminophen or dextromethorphan as needed for symptoms. The studies were conducted from August through November 2000 and enrolled a total of 2,096 subjects including 1,363 (65%) with laboratory-confirmed picornavirus infection. Time to alleviation of symptoms was significantly shorter for the pleconaril group compared to placebo in both studies, with median treatment benefits of 0.6 days (6.6 compared to 7.2 days, P=0.037) and 1.5 days (6.2 compared to 7.7 days, P=0.001) separately and 1.0 days (6.3 compared to 7.3 days, P<0.001) in a pooled analysis. Pleconaril-treated subjects also had improvements in time to resolution of individual symptoms and time to self-assessed “no cold” status ([Hayden et al. 2003](#)). Subjects who used symptom relief medication prior to enrollment had longer times to alleviation of symptoms. It is unclear whether the symptom relief medication use was the result of more severe symptoms or if the prolonged symptoms were the result

of suppression of cytokines and resulting prolonged viral replication ([USDHHS FDA Division of Antiviral Drug Products 2003](#)).

Vapendavir

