## 11. EFFICACY

### 11.1. General

Unless otherwise specified, all statistical tests will use two-sided tests at the  $\alpha=0.05$  level.

The following definitions will apply to multiple efficacy analyses:

Daily Diary Period	Each daily diary period will begin 24 hours prior to the time of diary assessment and end at the time of diary assessment.
Symptom Relief Medication	Any medication taken for a symptom of colds as indicated by the subject during the study period.

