### 11.2. Primary Efficacy Analysis: Time to Symptom Response

The primary efficacy analysis will be the comparison of the time from first dose of study medication to Symptom Response between treatment groups using Kaplan-Meier survival curves and a Gehan-Wilcoxon test stratified by (1) time from onset of illness to time of first dose of study medication (0-24, >24-≤36, or >36 hours from onset), (2) pre-enrollment use of symptom relief medication, and (3) presence of underlying lung condition including asthma, COPD, or past or present history of smoking. Separate Symptom Response definitions will be determined for ITTI subjects with no underlying lung condition and for ITTI subjects with underlying lung conditions. Time to Symptom Response will be calculated in the same way for the two groups and all ITTI subjects will be analyzed together.

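### Exploratory placebo-only comparisons by symptom relief medication use drop pre-enrollment use, a plausible confounder, for a reason that does not fit the SAP's own definitions

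*SAP*

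**What the plan says.** SAP 11.6.2 (time to Symptom Response) and 11.6.3 (time to Ability to Perform All Normal Activities) repeat the main time-to-event analyses within the placebo group, in both the infected and the all-treated populations. The contrast is users against non-users of symptom relief medication.

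- Both sections add a two-class factor, "Sum of baseline FLU-PRO symptom assessments", cut at 42. Because they repeat the stratified tests, they also inherit onset time and lung condition.
- Both sections remove one inherited stratum: "Pre-enrollment symptom relief medication use will not be used as a factor in the analysis". The reason given is "since the groups being compared are classified by symptom relief medication use".
- SAP 11.6.4 compares complications between the same groups with Fisher's exact test and no factor.

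Three other places bear on this:

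- SAP 11.1 defines symptom relief medication as "Any medication taken for a symptom of colds as indicated by the subject during the study period". SAP Tables 6 and 7 select it from the concomitant-medication listing, and SAP 10.1.5 limits concomitant medication to administration from the date of first study drug onward.
- SAP 11.2 lists "pre-enrollment use of symptom relief medication" as its own stratification factor, and Protocol Sections 3 and 6 stratify randomization by it.
- Protocol 1.1.1, on the Phase 3 pleconaril trials, reports: "Subjects who used symptom relief medication prior to enrollment had longer times to alleviation of symptoms". It then cautions: "It is unclear whether the symptom relief medication use was the result of more severe symptoms", or whether the medication itself prolonged the illness.

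**The concern.** The reason for removing the factor would be sound if the grouping variable and the factor were the same. SAP 11.5.10 to 11.5.12 drop onset time on that kind of ground, correctly, because each subgroup lies in one onset category. In 11.6.2 and 11.6.3 the two variables differ. A subject may medicate before enrollment and not afterwards, or the reverse.

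Placebo users and non-users are not formed by randomization. If pre-enrollment users recover more slowly and also medicate more on study, on-study users will look worse even when the medication does nothing. The stated exploratory objective is to evaluate the impact of symptom relief medication, so such a difference could be read as harm. In 11.6.4 nothing is balanced at all, although Protocol 8.3 counts asthma and COPD exacerbations among the complications and lung condition is already a recorded stratum.

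**Working it through.** The documents give no figure for these analyses, so there is none to reproduce. The check asks how large the distortion could be.

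**Inputs from the documents.** Two-sided 5% tests. Placebo infected population about 600/2 = 300. Placebo all-treated population up to 1,750/2 = 875 (800 was simulated). Placebo median 302.0 h (Protocol Table 7, normal activities). Censoring at day 21.

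**Assumed inputs.** Pre-enrollment use 50%. On-study use in pre-users/others 60/40%, 80/40% or 90/30%. Recovery hazard ratio (HR) for pre-use 1.0 to 0.7, and 0.8 for a high baseline score. Exponential times. Complications 12% in pre-users and 5% in others. On-study use fixed at the start, with no true effect.

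**Step 1: imbalance.** With 50% pre-use, the share of pre-users is a/(a+b) among on-study users and (1−a)/((1−a)+(1−b)) among non-users, where a and b are the two on-study use rates.

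- 60/40%: 0.60 against 0.40, difference 0.20
- 80/40%: 0.8/1.2 = 0.667 against 0.2/0.8 = 0.25, difference 0.417
- 90/30%: 0.9/1.2 = 0.75 against 0.1/0.8 = 0.125, difference 0.625

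**Step 2: spurious effect.** To first order, apparent HR ≈ exp(difference × ln HR).

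- 60/40%, HR 0.9: exp(0.20 × −0.105) = 0.98
- 80/40%, HR 0.8: exp(0.417 × −0.223) = 0.91
- 90/30%, HR 0.7: exp(0.625 × −0.357) = 0.80

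For complications the spurious difference is (12 − 5) × imbalance = 1.4, 2.9 and 4.4 percentage points.

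**Step 3: false-positive rate.** Simulated Gehan-Wilcoxon test stratified as planned (onset × lung condition × baseline score), without pre-enrollment use. There were 600 runs per cell, so the Monte Carlo standard error near 5% is √(0.05 × 0.95/600) = 0.9 points.

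| On-study use | Placebo n | HR 0.9 | HR 0.8 | HR 0.7 |
|---|---|---|---|---|
| 60/40% | 300 | 4.0% | 5.7% | 6.7% |
| 80/40% | 300 | 6.7% | 8.5% | 13.3% |
| 90/30% | 300 | 6.5% | 10.7% | 22.7% |
| 60/40% | 800 | 5.2% | 7.3% | 10.8% |
| 80/40% | 800 | 8.5% | 14.7% | 25.7% |
| 90/30% | 800 | 9.3% | 27.8% | 51.3% |

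At HR 1.0 the rate was 4.2–6.7%. With pre-enrollment use added as a stratum it was 3.3–6.8% in every cell. A second simulation used Weibull times, 1,500 trials per scenario and baseline severity as the only other stratum. At HR 0.75 and 80/40% use it gave 13.1% without and 5.0% with the factor (n = 300), and 26.0% and 4.9% (n = 875).

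**Step 4: complications.** Unadjusted Fisher's test rejected in about 6–7%, 9–13% and 20–25% of runs at n = 300 for the three use patterns, and about 8%, 27–29% and 53–56% at n = 800. A Cochran-Mantel-Haenszel test stratified by pre-enrollment use gave 3.5–7.3%. Confounding by lung condition was not simulated.

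**Step 5: what adjustment cannot cure.** SAP 11.2 grants Symptom Response only with two medication-free diary periods, so on-study use can delay the endpoint by definition. With users medicating for 1–7 days (n = 300, 80/40% use), rejection was 9.8% without and 6.8% with the factor at HR 1.0, and 19.3% and 7.5% at HR 0.8.

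**The case against.** The strongest reply has four parts.

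1. **Exposure window.** SAP 11.6.2 does not restate when use counts. If it meant pre-enrollment use, the SAP's reason would be right. If it meant any use before or during the study, the pre-use stratum would hold only users and add nothing to the test. SAP 11.1 and the concomitant-medication source point against both readings, but the silence is a defect worth correcting.

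2. **Is it a confounder?** A reader might infer that pre-enrollment use is an established confounder. The documents support only half of that: an association with outcome, of unstated size, in trials of another drug. No passage links pre-enrollment use to on-study use. Protocol 1.1.1 also leaves open whether pre-use marks severity, which the baseline score partly captures, or itself prolongs illness. Neither possibility justifies leaving it uncontrolled when the contrast is on-study use.

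3. **Existing adjustment.** A reader might also infer that lung disease is uncontrolled throughout. That is true only of 11.6.4. In 11.6.2 and 11.6.3 the issue is residual confounding.

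4. **Sparse complications.** Protocol Section 3 expects too few complications to show treatment differences. A stratified test with many cells would be thin. This stands, and it limits how many strata 11.6.4 can carry.

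**Conclusion.** The point holds in a limited form. The reason for dropping pre-enrollment use does not fit the SAP's definition of the grouping variable, and the factor is a collected randomization stratum that the protocol reports as prognostic. Under the assumptions above, the false-positive rate at 300 placebo subjects lies between about 5% with weak links and 23% with strong ones. It is higher in the larger all-treated placebo group, and the bias makes users look worse. SAP 11.6.4 is open to the same distortion and to imbalance in lung condition.

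Two stronger conclusions are not supported. The documents do not show that these analyses will report a medication effect that does not exist: the sizes are assumed, and inflation is negligible if either link is weak. Nor would restoring the factor make the comparison causal, since exposure arises after baseline and the endpoint itself requires medication-free periods.

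Severity is low. These are exploratory analyses with no nitazoxanide comparison, outside the hierarchy in SAP 11.4.

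**What to change.** - In SAP 11.6.2 to 11.6.4, state that the groups are defined by on-study use, and give the window. Start it at the time of first dose, because SAP 10.1.5 classifies by date and Day 1 spans both sides of enrollment.
- In 11.6.2 and 11.6.3, delete the sentence removing pre-enrollment use and keep it as a stratum beside onset time, lung condition and baseline FLU-PRO sum.
- In 11.6.4, use an exact Cochran-Mantel-Haenszel test stratified by lung condition and pre-enrollment use, with Fisher's test as supportive. Protocol 8.4.1 already names the Cochran-Mantel-Haenszel test for this endpoint in the treatment comparison.
- Label all three results as descriptive associations.

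The cost is a wording change and small program changes, with no new data. Strata become sparser. In 300 placebo subjects the time-to-event strata go from 3 × 2 × 2 = 12 (average 25 subjects) to 24 (average 12.5). Limiting 11.6.4 to 2 × 2 = 4 strata keeps an average of 75.
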